6.3.2. Patient/Observer Reported Outcomes Endpoints

6.3.2.1. Change from Baseline in Peak Pruritus NRS Over Time - for Participants ≥ 12 Years

- Analysis Set: FAS (see [Section 4](#)).
- Analysis Methodology: Descriptive statistics (see [Section 5.2](#)) and 95% two-sided confidence intervals for the mean for observed data and change from baseline in Peak Pruritus NRS over time - for participants ≥ 12 years.

6.3.2.2. Changes from Baseline in Patient Reported Itch Severity Scale Over Time - for Participants ≥ 6 Years and < 12 Years

- Analysis Set: FAS (see [Section 4](#)).
- Analysis Methodology: Descriptive statistics (see [Section 5.2](#)) and 95% two-sided confidence intervals for the mean for observed data and changes from baseline in Patient Reported Itch Severity Scale over time - for participants ≥ 6 years and < 12 years.

6.3.2.3. Change from Baseline in Observer Reported Itch Severity Scale Over Time - for Participants < 6 Years

- Analysis Set: FAS (see [Section 4](#)).
- Analysis Methodology: Descriptive statistics (see [Section 5.2](#)) and 95% two-sided confidence intervals for the mean for observed data and change from baseline in Observer Reported Itch Severity Scale over time - for participants < 6 years.

6.3.3. Pharmacokinetics

- Analysis Set: PK analysis set (see [Section 4](#)).
- Analysis Methodology: Descriptive statistics including number, mean, median, standard deviation, CV(%), minimum, maximum and the number of concentrations above the lower limit of quantification, for predose (C_{trough}) plasma concentrations of crisaborole and its identified main oxidative metabolites (AN7602 and AN8323).

6.4. Subset Analyses

Summary statistics for % change from baseline in EASI, achievement of improvement in ISGA, achievement of success in ISGA will be presented by subgroup below.

- Age (years) group (2-11, 12-17, < 18 , ≥ 18).

Descriptive statistics and 95% confidence intervals will be presented for each defined category of each subgroup.

6.5. Baseline and Other Summaries and Analyses

6.5.1. Baseline Summaries

Demographics will be summarized according to CaPS (CDISC and Pfizer Standards).

6.5.2. Study Conduct and Participant Disposition

Subjects evaluation, disposition and discontinuation will be summarized according to CaPS.

6.5.3. Study Treatment Exposure

Descriptive statistics (number, mean, standard deviation, median, minimum, maximum) and categorical summary will be reported for duration of treatment (time from the first to the last dosing date of treatment) and total number of applications. Amount of drugs used will be summarized descriptively (number, mean, standard deviation, median, minimum, maximum).

Descriptive statistics (mean, median, minimum, maximum) and categorical summary for number of treatment cycles started per participant will be reported. The same analyses will be conducted for number of Off-Treatment Cycles per participant. In addition, number and percentage of participants with Off-Treatment will be summarized by treatment cycle and all treatment cycles.

The subgroup analysis by age (<18, ≥18) will be conducted.

6.5.4. Concomitant Medications and Nondrug Treatments

Concomitant drug and non-drug treatment will be summarized according to CaPs. Number of days when rescue medication is taken will be descriptively summarized for All-Treatment Period, respectively.

6.6. Safety Summaries and Analyses

Safety analysis will be based on the safety analysis set. Safety data will be presented in tabular and/or graphical format and summarized descriptively, where appropriate.

6.6.1. Adverse Events

The safety data will be summarized in accordance with CaPS. All safety data will be summarized descriptively through appropriate data tabulations, descriptive statistics, categorical summaries, and graphical presentations. The subgroup analysis by age (<18, ≥18) will be conducted, where appropriate. Safety endpoints for the study include:

- Treatment-emergent AEs and SAEs;
- Withdrawals from active treatment due to AEs;

TEAEs and SAEs occurred in the treatment area will be summarized. Location of skin lesions will be listed.

It should be recognized that most studies are not designed to reliably demonstrate a causal relationship between the use of a pharmaceutical product and an adverse event or a group of adverse events. Except for select events in unique situations, studies do not employ formal adjudication procedures for the purpose of event classification. As such, safety analysis is generally considered as an exploratory analysis and its purpose is to generate hypotheses for further investigation.

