## **4. STUDY DESIGN**

### **4.1. Overall Design**

This study is a Phase 3, multicenter, open-label, long-term safety extension study of Studies C3291032 and C3291031 in Japanese pediatric and adult participants with mild to moderate AD to support the registration of crisaborole in Japan. After completion of the study intervention period in Study C3291032 or Study C3291031 and confirmed Study C3291027 eligibility, participants will be offered participation in the study from investigator sites in Japan. The sample size of this study is approximately 150 participants but will be determined by the number of participants who complete Study C3291032 treatment period or Study C3291031 treatment period and meet eligibility criteria of this study. Scheduled study visits will occur every 4 weeks (1 cycle) with On-Treatment or Off-Treatment cycles to be decided by the investigator based on the ISGA score. PK blood sampling will be conducted at the selected study sites for the participants aged between 2 years old and 11 years old at the time of signing the ICD in Study C3291032.

When the investigator assessment of ISGA is Almost Clear (1) or greater, an On-Treatment Cycle will be initiated. When the investigator assessment of ISGA is Clear (0), crisaborole ointment, 2% treatment will not be initiated and the participant will enter an Off-Treatment Cycle. Based on the ISGA score throughout the study, a participant may be administered a variable number of cycles of crisaborole ointment, 2% treatment (On-Treatment Cycle) during their up to 52 weeks of study participation.

On Week 56 (End of Study), a follow-up telephone call will be made by site staff to assess for AEs that may have occurred since the last visit.

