### **4.3. Justification for Dose**

In this study, the participants will apply crisaborole ointment, 2% BID during On-Treatment Cycle.

Crisaborole ointment, 2% BID is selected as the highest well-tolerated dose to maximize the potential for efficacy with minimal safety risk based on the results of foreign clinical studies, and 2% was technically the maximum dose for ointment formulation. In addition, the descriptive comparison of BID and QD regimens in Japanese AD patients was conducted in Study C3291028, crisaborole ointment, 2% BID was more effective than crisaborole ointment, 2% QD for Japanese adults and pediatrics participants. Regarding safety, crisaborole ointment, 2% BID was safe and tolerable for both Japanese adults and pediatric participants. Parent studies C3291032 and C3291031 are conducted using crisaborole ointment, 2% BID.

This study also has Off-Treatment Cycle to evaluate long term safety and efficacy of crisaborole in a condition close to real world clinical practice.

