### 6.1.1. Administration

For this study, the investigational product is crisaborole ointment, 2%. Crisaborole ointment, 2% is formulated to contain PF-06930164 (2%), white petrolatum, propylene glycol, mono- and diglycerides, paraffin wax, butylated hydroxytoluene, and edetate calcium disodium.

Ointment should be applied as an even layer of approximately 3 mg/cm^2.

[figure not shown]
The tool to standardize the calculation of the amount of ointment required for each participant will be provided by the sponsor to the study sites, which is based on each participant's own AD %BSA adjusted by height and weight.

The investigator will determine whether the participant will receive crisaborole ointment, 2% (Figure 1), specified as follows:

- If the participant is assessed as Almost Clear (1) or greater on the ISGA, the participant will begin a 4 week On-Treatment Cycle, with a sufficient quantity of crisaborole ointment, 2% tubes dispensed to the participant or his/her parent/legal guardian to meet anticipated use based on the investigator identified AD-involved areas. The investigator will review the dosing instructions with the participant or his/her parent/legal guardian. Study intervention administration will be performed BID at home.
- If the participant is assessed as Clear (0) on the ISGA, treatment **will NOT** be initiated and the participant will begin a 4-week Off-Treatment Cycle, during which the participant is allowed to use emollient(s)/moisturizer(s) in all areas (AD-involved and uninvolved), as needed.

Any new lesion(s) that develop during an On-Treatment Cycle should also be treated.

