**Figure 1. Diagram of Study Intervention Allocation by Visit**

**If a participant has AD that becomes intolerable:**

- If a participant has AD that becomes intolerable during an On-Treatment Cycle, the investigator may instruct the participant or his/her parent/legal guardian to discontinue crisaborole ointment, 2%. After study intervention discontinuation, weak- to strong-potency topical corticosteroids and/or topical calcineurin inhibitors could be prescribed up to 28 days based on clinical judgment is permitted (refer to Section 6.5.3).
- If a participant has AD that becomes intolerable during an Off-Treatment Cycle and cannot wait for the next scheduled visit to be treated by crisaborole ointment, 2%, the participant or his/her parent/legal guardian will be instructed to contact the study site to arrange an Unplanned Visit to initiate a regimen of crisaborole ointment, 2% BID for the remainder of a given 4 weeks interval. Depending upon the participant's AD condition, a weak- to strong-potency topical corticosteroids and/or topical calcineurin inhibitors could be prescribed directly based on clinical judgment by the investigator. Topical corticosteroids and topical calcineurin inhibitors must not be used on the same lesions concurrently, crisaborole ointment, 2% and topical corticosteroids or topical calcineurin inhibitors must not be used concurrently. In this case, the procedure for rescue treatment

during an Off-Treatment Cycle follows the instruction given for participants using rescue medication during an On-Treatment Cycle (refer to Section 6.5.3).

- At any treatment cycle, participant will be discontinued from the study when she/he requires prohibited medication usage or continuous rescue medication treatment >28 days.

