### **6.5.3. Rescue Medicine**

For participants with ISGA score >1 (i.e., mild, moderate or severe), crisaborole ointment, 2% therapy may be discontinued per investigator judgment to allow initiation of weak- to strong-potency topical corticosteroids and/or topical calcineurin inhibitors as rescue therapy for up to 28 days, after which crisaborole ointment, 2% BID may be restarted. Participants who continuously use topical corticosteroids or topical calcineurin inhibitors treatment >28 days will be discontinued from the study. The rescue medication prescription and relevant assessment should be recorded in the participant's source documents and in the CRF. Crisaborole ointment, 2% and topical corticosteroids or topical calcineurin inhibitors must not be used concurrently. Topical corticosteroids and topical calcineurin inhibitors must not be used on the same lesions concurrently.

Participant or his/her parent/legal guardian will be instructed on the dosage and administration requirements for any topical corticosteroids and/or topical calcineurin inhibitors prescribed by the investigator during the study. Instruction should follow the approved labeling for the indication and the product package insert, if provided.

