3.5.1. Adverse Events

An adverse event (AE) is considered a TEAE if the event started during the effective duration of treatment.

All events that start on or after the first dosing day and time/start time of this study, if collected, and before end of study will be flagged as TEAEs. The algorithm will not consider any events that started prior to the first dose date of this study. If an AE starts on the same day as the first dose date of this study, it will be considered treatment emergent unless the case report form (CRF) data indicates otherwise via explicitly recording time for AE onset and treatment dosing.

The effective duration of treatment starts at the date of the first dose of study treatment of this study and ends at the date of the last dose of study treatment plus the lag time.

If any AEs are ongoing at the time of the End of Treatment visit within the parent study and the participant is enrolling into this study, such AEs will be transcribed and followed within this study. AE updates following the parent study End of Treatment visit date will only be made within this study for participants who enroll into this study.

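### Treatment-area adverse events are not separated by whether the participant was on crisaborole, off treatment or on rescue at onset

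*SAP*

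**What the plan says.** **Three states within one participant.** Protocol 4.1 runs the study in 4-week cycles "with On-Treatment or Off-Treatment cycles to be decided by the investigator based on the ISGA score". A score of 1 or more starts an On-Treatment Cycle. For a score of 0, Protocol 6.1.1 says: "If the participant is assessed as Clear (0) on the ISGA, treatment will NOT be initiated". If disease becomes intolerable, crisaborole may be stopped and "weak- to strong-potency topical corticosteroids and/or topical calcineurin inhibitors could be prescribed up to 28 days based on clinical judgment". Protocol 6.5.3 describes this "as rescue therapy for up to 28 days, after which crisaborole ointment, 2% BID may be restarted" and adds: "Crisaborole ointment, 2% and topical corticosteroids or topical calcineurin inhibitors must not be used concurrently".

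**Treatment-emergent rule.** SAP 3.5.1 gives two end points. Events from the first dose of this study and "before end of study will be flagged as TEAEs". The same section also ties a treatment-emergent event to an effective duration of treatment, from first dose to last dose plus a lag. No value is given for the lag.

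**Safety output.** SAP 6.6.1 states: "TEAEs and SAEs occurred in the treatment area will be summarized". The only split it mentions is age below 18 against 18 and over.

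**Reported elsewhere.** SAP 6.5.3 counts treatment cycles and Off-Treatment Cycles. SAP 6.3.1.9 gives the incidence of rescue use, and SAP 6.5.4 the number of rescue days. None of these is linked to adverse events.

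**Context.** SAP version 2 was issued because the study was terminated. It revised sections 6.4, 6.5.3, 6.5.4 and 6.6.1, citing few participants and brief exposure.

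**The concern.** Protocol 2.2.5 and 2.3.1 name application site reactions as the most common drug-related adverse events. The treatment-area table is therefore the main local-safety output of a study whose primary objective is safety. A rescue product may be applied to the same lesions while crisaborole is withheld, and a local reaction to it would appear in that table with nothing to mark it. The same holds for a local event that starts weeks into an Off-Treatment Cycle.

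Protocol 4.3 gives a reason for having such cycles: "This study also has Off-Treatment Cycle to evaluate long term safety and efficacy of crisaborole in a condition close to real world clinical practice". A reader who wants to know how local safety looked during off-drug time cannot find out from the planned tables.

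**Working it through.** No figure in the documents is in dispute, so the check is mainly textual.

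**1. Are the states distinct?** Yes. On and Off cycles are set by the ISGA score, and Protocol 6.5.3 bars concurrent use of crisaborole and rescue. Rescue time is therefore off-crisaborole time. Scalp treatment is separate: Protocol 6.5.2 allows topical corticosteroids or calcineurin inhibitors there, and crisaborole is not applied to the scalp.

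**2. Does the treatment-emergent rule see the states?** Take a hypothetical participant:
- crisaborole Days 1–28
- Off-Treatment Days 29–56
- crisaborole Days 57–63
- rescue Days 64–77
- crisaborole Days 78–84 (last dose Day 84)
- Off-Treatment from Day 85

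| Onset of local event | State at onset | Flagged, end-of-study reading | Flagged, last-dose-plus-lag reading |
|---|---|---|---|
| Day 10 | crisaborole | yes | yes |
| Day 45 | Off-Treatment | yes | yes |
| Day 70 | rescue | yes | yes |
| Day 200 | Off-Treatment | yes | only if lag ≥ 200 − 84 = 116 days |

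Gaps between doses are counted on either reading. The readings differ only after the last dose. Off-drug time before the first dose of this study is not affected, because earlier events are not flagged. Participants whose first cycle is Off-Treatment are still in the Safety Analysis Set (SAP section 4).

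**3. Does the treatment-area table restore the distinction?** No. It filters by location. The location itself is not refreshed in Off time: the Schedule of Activities records treatable areas at Day 1, at On-Treatment starts and at Unplanned Visits that start treatment, but not at Off-Treatment starts.

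**4. Can another planned output recover it?** No. SAP 6.5.3 measures duration from first to last dosing date, so it includes the gaps. Cycle counts and rescue days are separate summaries.

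**5. How large could it be?** This is an illustration, not an estimate. A full course has (365 − 1)/28 = 13 cycles. Let k of them be off drug, with per-cycle risks p_on and p_off.
- Share of expected events starting off drug = k·p_off / [(13 − k)·p_on + k·p_off]
- Pooled per-cycle risk = [(13 − k)·p_on + k·p_off] / 13

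Assume p_on = 5.6% and p_off = 3.6%, borrowed from the crisaborole and vehicle rates of drug-related application site reactions in Protocol 2.3.1.

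| k | Share starting off drug | Pooled per-cycle risk |
|---|---|---|
| 0 | 0% | 5.6% |
| 1 | 3.6/70.8 = 5% | 70.8/13 = 5.4% |
| 3 | 10.8/66.8 = 16% | 66.8/13 = 5.1% |
| 6 | 21.6/60.8 = 36% | 60.8/13 = 4.7% |

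Off-drug events can only raise, or leave unchanged, the crude percentage of participants with a treatment-area event. Off-drug time with a lower risk dilutes a per-cycle rate. The direction therefore depends on the measure.

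The inputs are weak. They are whole-trial drug-related proportions used as per-cycle risks, vehicle stands in for no drug, rescue reactions are not modelled, and 13 completed cycles do not describe a study stopped early.

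**6. Are the data there?** Yes. The protocol requires intervention start and stop dates (6.4), start and end dates of other treatments (6.5) and rescue prescriptions (6.5.3).

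**The case against.** Four arguments go the other way.

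- **Termination.** With few participants and short exposure, a table by state may be nearly empty. This stands. It limits the practical effect and is why a listing may be enough.
- **Causality assessment.** Protocol 10.3.3 requires the investigator to judge relatedness for every event, weighing concomitant therapy and timing, and SAP 6.6.1 calls its safety analysis generally exploratory. This stands in part. Relatedness can separate some rescue reactions, but in an open-label single-arm study it is a judgment, whereas state at onset is a fact already recorded.
- **Sponsor standards.** Adverse event summaries follow CaPS, which is not among the documents and might add a split. That is possible, but the SAP does not specify one.
- **Real-world intent.** Protocol 4.3 wants the on/off regimen evaluated as used. This stands for pooled summaries, including by-visit efficacy.

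The last point bears on a stronger inference that a reader might draw: that pooled EASI and ISGA results by visit are wrong and should be split or limited to on-drug visits. The documents do not support that. Efficacy is exploratory and descriptive, and Off counts and rescue use are reported. Entry to an Off-Treatment Cycle requires a score of 0, so an on-drug-only summary would remove responders and be biased by selection.

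**Conclusion.** The point holds as a gap in safety reporting. On either end point in SAP 3.5.1, local events that start during an Off-Treatment Cycle or rescue between doses are flagged as treatment-emergent, and SAP 6.6.1 does not distinguish them from events on crisaborole. After the last dose, the two end points disagree and the lag is undefined.

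The size cannot be estimated from the documents, which give no frequency of off-drug or rescue time. It is nil without such time and likely small in the terminated study.

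Two further inferences are not supported:
- **That the crisaborole local-reaction rate is inflated by a known amount.** The 5.6% in Protocol 2.3.1 is a drug-related rate, while the treatment-area summary has no stated relatedness restriction. The two are not comparable, and no rescue reaction rate is given.
- **That off-drug events are presented as caused by crisaborole.** They are labelled treatment-emergent, which says nothing about cause.

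The conclusion assumes that CaPS adds no split by state and that the recorded dosing dates identify each interruption.

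**What to change.** **SAP 3.5.1.** Reconcile the two end points and state the lag in days.

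**SAP 6.6.1.** Keep the all-period table. Add state at onset to the treatment-area table, or to a listing if numbers are too small, in three categories:
- crisaborole, including the stated lag
- Off-Treatment
- rescue with crisaborole stopped

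Derive the state from the recorded dosing and rescue dates, leaving scalp-only treatment out of the rescue category. The lag is needed so that a delayed crisaborole reaction is not moved to another column. Its length matters. If it matched the 28-day minimum for adverse event collection in Protocol 8.3.1, a single 4-week Off-Treatment Cycle, or a rescue course of up to 28 days begun at once, would fall wholly inside it and the split would show nothing. Events inside the lag that start during Off or rescue time should therefore be marked, for instance by days since last application.

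**Treatment area in Off-Treatment Cycles.** Use the most recently recorded treatable areas, and say so.

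**SAP 6.3.1.** Leave by-visit efficacy pooled and label it as describing the on/off regimen regardless of rescue. A display by preceding state is optional and descriptive only.

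**Cost.** One derived variable, one added column or listing, and no new data. The downside is small cells.

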7. INTERIM ANALYSES

7.1. Introduction

No formal interim analysis will be conducted for this study.

7.2. Interim Analyses and Summaries

As this is an open-label, long-term extension study, the sponsor may conduct reviews of the data during the course of the study for the purpose of internal decision making, due to regulatory requests, or to support regulatory submissions. The data cutoff may occur after 6-month follow-up data across this study and the parent study has been accumulated for approximately 100 participants enrolled in this study.

This study will use a data monitoring committee (DMC). The DMC is independent of the study team and includes only external members. The DMC charter describes the role of the DMC in more detail.

The DMC will be responsible for ongoing monitoring of the safety of participants in the study according to the charter. The recommendations made by the DMC to alter the conduct of the study will be forwarded to the appropriate Pfizer personnel for final decision. Pfizer will forward such decisions, which may include summaries of aggregate analyses of safety data, to regulatory authorities, as appropriate.

